Study Protocol and Statistical Analysis Plan**Title of study:** Babies' Expectations About Racial Interactions**NCT number:** NCT05324007**Date of document:** May 31, 2022

Table of contents

| | Page Number |
|--------------------------------|-------------|
| Study Protocol..... | 3 |
| Objectives..... | 3 |
| Design..... | 3 |
| Methods..... | 3 |
| Statistical Analysis Plan..... | 6 |
| References..... | 7 |

Study Protocol

Objectives: The ability to categorize people into social groups is thought to arise early in human development (Liberman et al., 2017b). Language and race are often considered salient social categories that adults use to categorize and discriminate people. Infants also use language as a meaningful and inductive category: extensive research indicates that infants show preferences based on language (Kinzler et al., 2007; Pun et al., 2018) and infer communicative and social relationships based on language groups (Liberman et al., 2017a). In contrast, less is known about whether infants use race as a meaningful social cue. Past research has focused on infants' perceptual categorization skills that suggest infants can use race to make perceptual distinctions: For example, at 3 months of age, infants prefer to look at faces of people from their own-race (or races they are familiar with) over other-races (or races they are not familiar with) (Kelly et al., 2005). However, less is known about whether infants use race as an inductive social category. The current study therefore examines whether infants use race to predict social relationships as they do for language.

In the following, racial outgroup individual indicates an individual who is of a race that is different from the races of the infants' primary caregivers or parents. Racial ingroup individual indicates an individual who is of the same race as the infants' primary caregivers/parents.

Design: The study will be conducted online on a platform called Lookit (lookit.mit.edu), in which participants can log on to this website to complete the study. The study will last about 10 minutes with parents providing consent via recorded videos, having their infants watch video stimuli, and then completing a demographic questionnaire after their infants finish watching the video stimuli. While infants watch the video stimuli, they are recorded via a webcam that is safely stored and accessible only by researchers. See <https://lookit.readthedocs.io/en/develop/index.html> for more details about this online platform.

The design of the study is based on Liberman et al. (2017a) but adapted for an online format. Infants will be randomly assigned to one of three conditions: (1) Black-White, (2) Black-Black, and (3) White-White. Black-White condition will consist of one White female and one Black female individual. White-White condition will consist of two White female individuals and Black-Black condition will consist of two Black female individuals. In total, there are four different White and three different Black actors. The pairings between the two actors will be counterbalanced across infants such that each actor will be presented in all conditions.

Methods:

Sample & recruitment. We will recruit infants between the age of 8 months;1 day to 15 months;1 day. No participant will be excluded on the basis of sex/gender or race and ethnicity. All participants – regardless of sex/gender, race, and ethnicity – will be randomly assigned one of the three conditions. Participants will be recruited from the Lookit participant database, in which families have voluntarily signed up to be contacted for studies in which their children are eligible for on the the platform. In addition, we will recruit from an existing University of Chicago Center for Early Childhood Research (CECR) participant pool (<http://babylab.uchicago.edu>). The participant pool has over 4000 children that range in age from birth to school age. Currently,

the participant pool has 76 eligible infants in our targeted age range, but infants are consistently aging into this age range and year-round recruitment efforts are conducted such that typically our laboratory have successfully completed testing of 100 to 150 infants within a year. We have a strong track-record of recruiting and testing infants from racially and linguistically diverse backgrounds. Participants are typically contacted through phone or email by trained research assistants to participate in the study. Recruiting from these established participant pool typically results in ~50% inclusion of females. The racial and ethnic composition of the sample is expected to reflect the composition of the U.S. To ensure we continue to recruit a representative percentage of minority children, we will carefully monitor enrollment and include more recruitment efforts to cater to minority children as needed.

Procedure. Parents who have indicated they are willing to be contacted for studies from the database with infants in the eligible age range will be emailed a link to the study to participate. The parents can then click on the link and follow the instructions on screen to read about the description of the study and a consent document. If the parents decide to participate, they will be instructed to read the consent form and provide online permission by recording a video of themselves reading a statement, “I have read and understand the consent document. I am this child’s parent or legal guardian and we both agree to participate in this study.” Because the infants are not able to provide assent, no assent was obtained. Parents will have the option to download and/or print the forms to retain a copy for their files. Only participants with a valid consent will be permitted to participate in the study.

Participants will be randomly assigned to one of the three conditions: (1) Black-White, (2) Black-Black, and (3) White-White. In all conditions, infants will first view familiarization then test trials. In the familiarization trials, infants will begin by viewing four trials of familiarization. The familiarization trials will consist of two female actors facing forward and talking about infant-friendly topics like the weather, grocery shopping, school, or stars in a neutral-positive speech. The order in which actors speak and their pairings will be counterbalanced across participants. Each trial will last 10.5 seconds and be repeated four times. After familiarization, infants will view six test trials. Three of these test trials will be affiliation trials and three will be disengagement trials. In the affiliation trial, the two actors start by facing forward, turn to face each other, and then wave at each other saying “Hi!”, while smiling. In the disengagement trial, the actors start by facing forward, turn to face each other, and then make a “Hmph!” sound and turn their backs to one another. Both types of trials have the same overall length of the interaction and the actors maintained the same distance from each other throughout the trial so that they were the same distance apart during both affiliation and disengagement. Each test trial will last 3 seconds, with a still image of the actors for 15 seconds after the trial ends. Each test trial therefore will last 18 seconds. This length is in line with the maximum 20 second test trial used by the case study on Lookit (Scott et al., 2017). The affiliation and disengagement trials will be presented in an alternating order and the order will be counterbalanced across participants. Looking time at the still images will be measured at each trial. After completing the trials, parents will complete a survey that asks basic demographic information and provided an option to complete an additional, optional social network questionnaire. In this demographic survey, parents will provide racial, ethnic, and linguistic information about themselves and their infants, as well as questions about their neighborhood trust and zip code in which the infant resides. Parents will also have an option to complete a

social network questionnaire about the people the infants see and interact with on a weekly and daily basis in the past month. Racial, ethnic, and linguistic demographic information about these individuals will be collected. Describe in detail below in *Measured variables* section.

Participants will be compensated \$5 (gift card) within approximately a week for their participation. If they complete the optional additional survey on infants' social network, they will be compensated an additional \$5. To be eligible for the gift card, the infant must be in the age range of the study (i.e., 8 months; 1 day – 15 months; 1 day) and the parent must provide and submit a valid consent statement. We will still provide compensation for the family even if they do not finish the study or we cannot use the infant's data.

Data will be excluded if we observe any parental interference during the study. We will include data as long as infants complete at least one affiliation and one disengagement trial to maximize including data as much as possible.

Measured variables.

We will use the following outcome variables: (1) Looking time during familiarization: We will record looking times during each 4 familiarization trials per infant. (2) Looking time during test trials: We will record the looking times during each 3 affiliation trials and 3 disengagement trials for each participant.

Demographic variables: (1) Infant race/ethnicity: One or more of the following categories can be used by the parent to identify their infant's race/ethnicity: American Indian or Alaska Native, Asian, Black or African American, Hispanic or Latino, White, Native Hawaiian or Other Pacific Islander, Other (which parents can specify any other race/ethnicity) (2) Infant language exposure: parents can select from the following categories: monolingual, exposure, bilingual/multilingual. Parents will also be asked to indicate what language(s) their infants are exposed to. (3) Parent education level: This will consist of 8th grade or less, 9th-12th grade no diploma, High school graduate or GED completed, Some college credit but no degree, Associate degree (AA, AS), Bachelor's degree (BA, BS, AB), Graduate or professional degree.

Exploratory variables: These measures were collected to explore questions about how infants' social environments may potentially relate to infants' looking patterns.

Neighborhood variables: (1) Infant's current zip code: This information will be used to derive neighborhood racial demographics, neighborhood median income, and neighborhood population density at the zip code level using the most recent American Community Survey (ACS) U.S. census data. (2) Neighborhood trust: This is a parent-reported measure of whether parents judge their neighbors as trustworthy. This value will be calculated by summing responses from the "social cohesion and trust" scale from (Sampson et al., 1997).

Social network variables: (1) Network racial entropy: This value will be calculated using the R package "entropy" using parent reported social network demographics and calculated for each participant. (2) Network racial EI Index: This value will be computed using the 'egor' package and will be calculated as follows: (the number of people who are from different racial backgrounds from the child) – (the number of people who are from the same racial backgrounds

as the child)/Network Size. (3) Network size: This value will be derived from parent reported social network demographics by counting the total individuals reported in the infants' network.

Statistical Analysis Plan:

Trained research assistants will view study videos to measure how long infants looked at the familiarization trials and test trials. These research assistants will be blind to the hypotheses of the study, will not know what condition the infants were assigned to, and will not have access to identifying information, including name and birthdate, when they are coding these videos.

Preliminary analyses. To check that attention during familiarization do not differ according to condition: A mixed ANOVA with trial number (first, second, third, and fourth) as a within-subjects factor, and condition (White-White, Black-Black, and Black-White), infants' age, and infants' sex as between-subjects factors will be run on looking time during familiarization. We predict that infants' attention will decrease as trial number increases in familiarization but no difference across conditions. To check that trial order, infants' age, and infants' sex does not influence infants' attention during test trials: A mixed ANOVA with test trial order (affiliation first or disengagement first), infants' age, and infants' sex as between-subject factor will be conducted. We do not expect any significant effects from these preliminary analyses as previously found in (Lieberman et al., 2017a). However, if any of the above factors are significant in relation to test trial looking time, we will include them as covariates in the following main ANOVA model.

Main analyses. A mixed ANOVA with condition (White-White, Black-Black, and Black-White) as a between-subjects factor and test trial number (first, second, or third) and test type (affiliation vs. disengagement) as within-subjects factors on the dependent variable of looking time during test trials will be conducted. If there is a significant interaction, each condition will be analyzed separately by performing the same repeated-measures ANOVA on test trial looking times for each condition with trial number and test trial type as within-subject factors.

References:

- Kelly, D. J., Quinn, P. C., Slater, A. M., Lee, K., Gibson, A., Smith, M., Ge, L., & Pascalis, O. (2005). Three-month-olds, but not newborns, prefer own-race faces. *Developmental Science*, 8(6), F31–F36. <https://doi.org/10.1111/j.1467-7687.2005.0434a.x>
- Kinzler, K. D., Dupoux, E., & Spelke, E. S. (2007). The native language of social cognition. *Proceedings of the National Academy of Sciences*, 104(30), 12577–12580. <https://doi.org/10.1073/pnas.0705345104>
- Liberman, Z., Woodward, A. L., & Kinzler, K. D. (2017a). Preverbal Infants Infer Third-Party Social Relationships Based on Language. *Cognitive Science*, 41(S3), 622–634. <https://doi.org/10.1111/cogs.12403>

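### Do the unused ingroup and outgroup definitions leave an own-group analysis missing from the plan?

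*Combined protocol and SAP*

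**What the plan says.** All references are to the combined protocol and SAP.

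- **Objectives.** The aim is given as "The current study therefore examines whether infants use race to predict social relationships as they do for language". Two terms are then defined for use in the rest of the text: "racial outgroup individual indicates an individual who is of a race that is different from the races of the" infant's primary caregivers or parents, with ingroup as the counterpart.
- **Design.** Pairs of actors are varied by race; for example, "Black-White condition will consist of one White female and one Black female individual". The other two conditions show two White or two Black actors.
- **Sample & recruitment.** "No participant will be excluded on the basis of sex/gender or race and ethnicity", and "The racial and ethnic composition of the sample is expected to reflect the composition of the U.S". No percentages and no planned sample size are given.
- **Procedure.** In the survey after the trials, "parents will provide racial, ethnic, and linguistic information about themselves and their infants".
- **Main analyses.** "A mixed ANOVA with condition (White-White, Black-Black, and Black-White) as a between-subjects factor", with test trial number and test type within subjects. A significant interaction leads to the same analysis within each condition.
- **Preliminary analyses.** Test trial order, age and sex are screened against test-trial looking: "if any of the above factors are significant in relation to test trial looking time, we will include them as covariates". Race is not among the factors screened.

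**The concern.** A term defined at the outset and then never used suggests that a planned analysis was dropped. Infants of every race are enrolled, so a White-White pair is ingroup for some infants and outgroup for others. A Black-White pair contains no ingroup actor for infants whose caregivers are neither Black nor White. If infants hold expectations mainly about people like their caregivers, the pooled interaction is diluted by the racial mix. A null result could then be misread as showing that infants do not use race at all, and any own-group analysis added later would be post hoc even though the protocol defines its terms.

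The nearest planned measure, the network racial EI index, does not fill this role. It compares the child with the people in the child's network rather than with the actors, it comes from an optional survey, and no model is named for it.

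**Working it through.** **Tracing the terms.** The plan has two preliminary ANOVAs, one main ANOVA and one per-condition follow-up. Their factors are familiarization trial number, condition, age, sex, test trial order, test trial number and test type. So 0 of 4 models use infant race, parent race or ingroup status, and the covariate rule cannot bring them in. The description of the text is correct.

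**Matching objective to test.** The objective concerns third-party relationships. Condition varies whether the two actors share a race, and test type varies whether they affiliate or disengage. The condition by test type interaction is therefore the test of the objective. It needs no information on the infant's own race to be valid.

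**What own-group dependence would cost.** The plan states no figure to reproduce, so this is illustration only. Assumptions: 150 infants (the top of the laboratory's typical 100 to 150 tested per year, which is not a planned size), 50 per condition; effects in SD of each infant's affiliation-minus-disengagement difference; no effect in Black-White pairs; caregiver shares pW (White) and pB (Black) as listed.

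For condition means m_j, the one-way F test on difference scores has noncentrality λ = 50 × Σ(m_j − m̄)², with 2 and 147 degrees of freedom.

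*Shared 0.5 SD effect in same-race pairs.* Means are 0.5, 0.5 and 0, so m̄ = 0.333 and λ = 50 × (0.0278 + 0.0278 + 0.1111) = 8.33. Power is 73% (simulation: 72 to 74%).

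*0.5 SD only when a same-race pair matches the caregiver.* Means are 0.5pW, 0.5pB and 0.

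| pW/pB (%) | Means | λ | Power, formula | Power, simulation |
|---|---|---|---|---|
| 60/13 | 0.300, 0.065, 0 | 2.49 | 27% | 26% |
| 50/15 | 0.250, 0.075, 0 | 1.65 | 19% | 18% |
| 50/25 | 0.250, 0.125, 0 | 1.56 | 18% | 17% |
| 40/30 | 0.200, 0.150, 0 | 1.08 | 14% | 14% |

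The simulations used 3,000 runs per scenario. In them, a secondary term for a same-race pair matching caregiver race, adjusted for condition and caregiver race, reached 41, 43, 52 and 55% across the same four mixes.

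*Opposite signs, +0.4 SD for matching pairs and −0.4 SD for the rest.* The same-race means are 0.4(2pW − 1) and 0.4(2pB − 1). Both are zero only at 50/50. If infants matching neither race show no effect, the means are 0.4(pW − pB) and its negative, which vanish at any equal split. Full cancellation thus needs both a sign reversal and equal White and Black shares.

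**What an added model could deliver.** Under the listed mixes the Black-Black condition would hold 50 × 0.13 = 6.5 to 50 × 0.30 = 15 infants with Black caregivers. A second term, for Black-White pairs in which one actor matches the caregiver, has 22 to 26% power at 0.5 SD. The pooled test has 36 to 46% in that same pattern. The second term cannot be estimated if every infant matches one actor race. It rejected in about 15% of runs when there was no mixed-pair effect but its assumption about non-matching infants failed.

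**The case for a change.** The strongest case for a change is that the protocol itself raises own-group dependence. It defines the terms, collects parent race, and cites own-race looking preferences at 3 months as background. When only ingroup same-race pairs carry an effect, the matching term clearly outperforms the pooled test, and naming it in advance would cost only SAP wording and one secondary model.

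Part of this stands. The terms are orphaned, the power loss is real under that pattern, and a null interaction would describe the average over the infants recruited, not each racial group.

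The rest does not. No hypothesis about the infant's own group is stated, and nowhere does the plan say that a null would mean infants ignore race. Reading a result as an average over the sample applies to any ANOVA without a moderator. If infants share one expectation, the added terms detect nothing (4 to 6% rejection) while the pooled test keeps its 72 to 74%. Whether to pre-specify a moderator with small cells is a matter of judgement. Parent race is collected, so an own-group analysis can still be run and labelled exploratory.

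**Conclusion.** The observation is accurate, but it does not show a fault in the analysis. Two definitions are never used, which is a clerical leftover. The main test is valid for the stated third-party question, and followed as written it estimates the average effect in the recruited mix. The possible cost is a fall in power from about 73% to between 14 and 27%. That arises only if expectations depend on the infant's own group in the way assumed, with 150 infants, a 0.5 SD effect and the racial shares listed. The documents supply none of these figures, so the calculation shows what could happen and does not measure this study's loss. No change to the plan follows.

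### No pre-specified contrast compares Black-White with the same-race pairs; the planned route is a joint three-condition interaction followed by separate per-condition analyses

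*Combined protocol and SAP*

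**What the plan says.** - Study Protocol, Objectives: "The current study therefore examines whether infants use race to predict social relationships as they do for language". No particular comparison of conditions is named.
- Study Protocol, Design: "White-White condition will consist of two White female individuals and Black-Black condition will consist of two Black female individuals"; Black-White has one actor of each race. On the cast: "In total, there are four different White and three different Black actors". On allocation of actors: "The pairings between the two actors will be counterbalanced across infants such that each actor will be presented in all conditions". The Procedure section adds: "The order in which actors speak and their pairings will be counterbalanced across participants".
- Statistical Analysis Plan, Main analyses: "A mixed ANOVA with condition (White-White, Black-Black, and Black-White) as a between-subjects factor and test trial number" and test type as within-subject factors, on test-trial looking time. If an interaction is significant, the same repeated-measures ANOVA is run within each condition. The plan does not say which interaction triggers this step. It specifies no contrast, pairwise comparison or pooling of conditions.
- Study Protocol, Procedure, on who is analysed: "We will include data as long as infants complete at least one affiliation and one disengagement trial".
- The documents give no target sample size, significance level, effect size or SD. The nearest figure, in Sample & recruitment, is laboratory throughput: "typically our laboratory have successfully completed testing of 100 to 150 infants within a year".

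**The concern.** The most direct test of the stated question is whether the affiliation-versus-disengagement difference for a Black-White pair departs from that for same-race pairs. The plan approaches this in two steps, and neither isolates it.

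The first step is an omnibus test. With three conditions, the condition by test type interaction has 2 df, and White-White versus Black-Black alone can make it significant. Those conditions have no actor in common, so a difference between them cannot be separated from who was filmed.

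The second step looks inside each condition. A result that is significant in one condition and not in another is not a test that the two differ. If infants in every condition look longer at the same test type, all three follow-ups can agree while Black-White really does depart. A real cross-race difference could be missed, and the reading of three separate results stays open until they are seen.

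**Working it through.** **Actors.** Four White and three Black actors give C(4,2) = 6 White-White pairs, C(3,2) = 3 Black-Black pairs and 4 × 3 = 12 Black-White pairs. A White actor can appear only in White-White and Black-White; a Black actor only in Black-Black and Black-White. So 0 of 7 actors can appear in all three conditions.

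**Why equal weights.** Let mean(W) and mean(B) be the average additive actor effects on the test-type difference. With pairings balanced within condition, White-White carries 2 × mean(W), Black-Black 2 × mean(B), and Black-White mean(W) + mean(B). Black-White minus 0.5 × (White-White + Black-Black) is then free of them, and no other weights achieve this. Effects specific to a particular pair do not cancel.

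**Which interaction.** Three factors (condition, trial number, test type) give four interactions: three two-way and one three-way. Only condition by test type addresses the question here.

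**Power.** There is no stated figure to reproduce. Assumptions, not in the documents: two-sided alpha 5%, complete data, SD 3 s for each infant's mean affiliation minus mean disengagement looking time, and n = 36 / 48 per condition (108 / 144 in total, inside the 100 to 150 throughput range). With complete data, the condition by test type F equals a one-way ANOVA on these difference scores.

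- Omnibus: noncentrality = n × Σ(μ − mean μ)² / SD², df 2 and 3(n − 1).
- Contrast: noncentrality = difference / (SD × √(1.5/n)), df 3(n − 1).

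*Black-White 1.8 s above both same-race conditions.* Σ = 1.2² + 0.6² + 0.6² = 2.16.
- Omnibus: 36 × 2.16/9 = 8.64 and 48 × 2.16/9 = 11.52; power 74 / 86%.
- Contrast: 1.8/(3 × √(1.5/36)) = 2.94 and 1.8/(3 × √(1.5/48)) = 3.39; power 83 / 92%.
- Sensitivity at n = 36, omnibus and contrast: SD 4 s, 48% and 59%; SD 2 s, 98% and 99%.

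*White-White +0.9 s, Black-Black −0.9 s, Black-White 0 s (true contrast 0).* Σ = 1.62; noncentrality 6.48 / 8.64.
- Omnibus significant in 61 / 74%; contrast in 5%.

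*Only one same-race condition shifted by 1.8 s.* The contrast's true value is 0.9 s in size.
- Omnibus 74 / 86%; contrast 31 / 39%.

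**Reading the follow-ups** (simulation, 40,000 replicates, same assumptions). Suppose Black-White counts as set apart when the omnibus test is significant and its follow-up result (positive, null or negative) lies strictly above both or strictly below both same-race results. This rule is an assumption; the SAP states none. Black-White is truly 1.8 s higher throughout:

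| Same-race level | Set apart, n = 36 / 48 | Contrast significant |
|---|---|---|
| 0 s | 70 / 82% | 83 / 92% |
| +1.0 s | 23 / 14% | 83 / 92% |
| +1.5 s | 3 / 1% | 83 / 92% |

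At +1.5 s, a significant omnibus test is followed by three matching follow-up results in 45 / 72% of studies.

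**False cross-race readings.** Now take a looser reading: a significant omnibus test plus a significant Black-White follow-up. With no condition difference, no shared preference and no actor variance, this occurs in 1.6% at either n. With Black-White +1.0, White-White +1.9 and Black-Black +0.1 s, the true contrast is 1.0 − (1.9 + 0.1)/2 = 0, yet it occurs in 30 / 46%.

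**The case against.** The strongest reply is that the condition by test type interaction is already a between-infant comparison of all three conditions. That is correct. A reader might infer that the plan contains no between-condition test at all, and the documents do not support that. What is missing is a test aimed at Black-White versus same-race pairs. Judged against the omnibus test alone, the gain from the contrast is moderate: 83 / 92% against 74 / 86%.

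Second, the lowest figures (23 / 14% and 3 / 1%) depend on a rule for reading the follow-ups that the SAP does not state. This stands, and they should be quoted only with that condition. Still, the SAP offers no other rule for moving from three within-condition results to a cross-race conclusion.

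Third, a reader might infer from the 61 / 74% figure that the plan would often yield a false cross-race finding. In that scenario the follow-ups set Black-White apart in only about 2%. The opposite inference, that the planned route can never mislead, is also too strong, as the 30 / 46% case shows.

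Fourth, the Objectives name no contrast, and the affiliation-versus-disengagement difference within a condition does measure what infants expect of that pair. That is a good reason to keep the per-condition analyses, but it does not supply the comparison.

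Finally, the actor sentence is probably a slip for each actor appearing in both conditions open to her. Nothing in the documents suggests that the stimuli or the random assignment are faulty.

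**Conclusion.** The point holds as a gap in pre-specification that is cheap to close. The plan tests condition jointly, does not name the interaction that triggers the follow-ups, and has no planned contrast of Black-White with the same-race pairs. The follow-ups cannot stand in for one.

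Under the assumed inputs, the contrast adds 9 / 6 percentage points of power over the omnibus test when only Black-White departs (83 − 74 and 92 − 86), and about 11 points at SD 4 s and n = 36 (59 − 48). Its larger advantage is that it does not depend on a test-type preference shared by all conditions, and it stays at 5% when Black-White lies midway between the same-race conditions. The sizes depend on the assumed SD, effect and sample size. The structural finding and the actor count depend only on the documents. The actor sentence is a minor wording error.

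**What to change.** 1. In Main analyses, name condition by test type as the interaction that triggers the per-condition analyses. Pre-specify a 1-df contrast: Black-White minus the equal-weight mean of White-White and Black-Black, on each infant's mean affiliation minus mean disengagement looking time over completed trials. This score exists for every infant kept under the inclusion rule. Name the contrast in advance as the test of the cross-race question. Keep the omnibus and per-condition analyses.
2. Report Black-White versus White-White and Black-White versus Black-Black estimates with confidence intervals beside the contrast. State that a significant contrast driven by only one same-race condition will not be read as Black-White differing from same-race pairs in general.
3. State that a White-White versus Black-Black difference is specific to the actors filmed and will not be read on its own as a race effect.
4. Reword the Design sentence: each actor appears in her same-race condition and in Black-White, with pairings balanced within condition.

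The cost is one contrast, two interval estimates and a few sentences; no new data are needed. The downside is the one-condition pattern. There the contrast is significant in 31 / 39% against 74 / 86% for the omnibus test, which is both lower power for that pattern and a possible misreading, hence item 2. The roles of the two tests must be fixed in advance: if either at 5% could support the same conclusion, the chance of rejection under the null is about 7.5%.
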